8.7.3.1 Safety Analyses

Safety will be assessed by close monitoring and timely assessment of adverse events (AEs), laboratory parameters (blood tests, urinalysis), vital signs (blood pressure, heart rate), subject's medical condition (physical examination including weight), general well-being and activities of daily life (Eastern Cooperative Oncology Group (ECOG) performance status). Each subject will be regularly assessed at each visit for potential AEs and disease related signs and symptoms. The CTCAE v5.0 will be used to grade toxicities / AEs.

The Safety population will be used for the analysis of safety endpoints.

Descriptive statistics (n, mean, standard deviation, median, minimum, and maximum) will be calculated for continuous variables. Frequencies and percentages will be presented for categorical variables.

Adverse Events:

Adverse events will be coded using the most recent version of Medical Dictionary for Regulatory Activities (MedDRA). Treatment Emergent AE's (TEAE) are defined as events with an onset on or after the first treatment. TEAEs will be summarized by study phase, treatment group, System Organ Class, and preferred term. The following TEAE summaries will be provided:

- Overall (i.e., regardless of severity or relationship to treatment)
- By severity grade (mild, moderate, severe, or life threatening for SAEs)
- By relationship to clinical trial treatment according to the mapping scheme below:
 - Potentially related: will include all adverse events with a relationship rating of “definitely”, “probably” or “possibly”.
 - Unlikely/not related: will include all adverse events with a relationship rating of “unlikely” or “unrelated”.

In addition, separate summaries of serious adverse events, and adverse events resulting in discontinuation of study treatment will be presented.

Clinical Laboratory Data

All laboratory values will be listed. Laboratory measurements will also be summarized as continuous variable and presented by treatment group and time point.

Physical Examination

All physical examination findings will be listed and/or summarized.

Vital Signs

All vital sign findings will be listed and summarized.

Electrocardiograms (ECGs)

All ECG findings will be listed and summarized.

Eastern Cooperative Oncology Group (ECOG) performance status

All ECOG performance status findings will be listed and summarized.

9 ADVERSE EVENTS (DEFINITIONS AND REPORTING)

The Investigator is responsible for the detection and documentation of events meeting the criteria and definition of an AE or SAE, as provided in this protocol. During the study when there is a safety evaluation, the Investigator or site staff will be responsible for detecting, documenting and reporting AEs and SAEs as detailed in this Section of the protocol.

9.1 ADVERSE EVENT (AE)

An adverse event (AE) is defined as any unfavorable or unintended sign, symptom, or disease that occurs or is reported by the subject to have occurred, or a worsening of a pre-existing condition. An adverse event may or may not be related to the study treatment.

AEs will be elicited through direct questioning and subject reports. Any abnormalities in visit evaluations, physical examination findings or laboratory results that the investigator believes are clinically significant to the research subject and that occurred after initiation of the first study treatment will be reported as AEs. Abnormal findings that are NOT clinically significant should not be recorded as an AE.

9.2 REPORTING AND FOLLOW-UP OF ADVERSE EVENTS

Report initiation for all AEs and serious adverse events (SAEs), (see [Section 9.3](#)), will begin at the time of the first treatment and continue up to the final study visit. All events will be followed to resolution or until 30 days after the subject completes the study. A final assessment of outcome will be made at that time.

All AEs must be recorded in the subject's medical records and on the CRF. AEs will be reported using customary medical terminology along with the following information: the onset and end dates, whether the event is considered to be a SAE (see [Section 9.3](#)), the impact the event had on study treatment (see [Section 9.2.1](#)), the CTCAE grade (intensity) of the event (see [Section 9.2.2](#)), the causality of the event (see [Section 9.2.3](#)), whether treatment was given as a result of the event (see [Section 9.2.4](#)), and the outcome of the event (see [Section 9.2.5](#)).

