A core or excisional biopsy may be necessary in order to evaluate the CCR5 receptor status of the cancer tumor by Immunohistochemistry (IHC) assay. This assay will be performed in archival tissue from previous biopsy specimens. If archival tissue is not available then, fresh core or excisional biopsy will be done. Serious complications related to core biopsy are rare. The commonest problem is bleeding, which is usually easy to control at the time of the procedure. Rarer complications of core biopsy include infection and abscess formation, pneumothorax, milk fistula formation, cosmetic deformity and seeding of tumor along the biopsy track. Compared to a needle biopsy, a surgical biopsy is more invasive, has a longer, more uncomfortable recovery time and has a higher risk of infection and bruising.

Unknown Risks

As with all research there is the remote possibility of risks that are unknown or that cannot be foreseen based on current information.

Theoretical risk for increased severity of West Nile virus infection

Individuals who lack a functional CCR5 gene are at increased risk for severe infection by West Nile virus [Thompson, 2009]. Because of this, treatment with CCR5 co-receptor antagonists poses a theoretical risk for increased severity of West Nile virus infection. However, this concern is mitigated by several factors. First, no increased risk was observed for individuals who possess one functional and one non-functional CCR5 gene, indicating that an intermediate amount of CCR5 is sufficient for defense against West Nile virus [Thompson, 2009]. Second, use of CCR5 co-receptor antagonists is unlikely to completely abrogate CCR5 function, and there has been no association reported to date between CCR5 co-receptor use and severe West Nile virus. Additionally, leronlimab (PRO 140) weakly antagonizes the natural activity of CCR5 and thus is less likely to adversely affect immune function. However, patients enrolled in this study may have immune suppression from chemotherapy and therefore, DSMB and the investigators will be alerted to risks of West Nile infections. Furthermore, this has not been established to be a risk with maraviroc, the other FDA-approved anti-CCR5 drug already.

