4.1 PRE-SCREENING PERIOD

4.1.1. Pre-Screening Visit

Sites are required to pre-screen subjects for study inclusion, evaluating CCR5 positive status by Immunohistochemistry (IHC) assay prior to performing a full screening visit. This assay will be performed in archival tissue from previous biopsy specimens. If archival tissue is not available then, fresh core or excisional biopsy will be obtained.

The subject will sign and date the pre-screening informed consent form (ICF) in-person or remotely prior to any study-related pre-screening procedures. The remote consenting will involve the site sending the pre-screening ICF to subject (via hard copy or email) to discuss the consent over the phone. The written informed consent must be signed and personally dated by the subject, sent back to the site and will then be signed by the person who conducted the informed consent discussion. The consent process and discussion over the phone will be captured in the medical records.

A unique identification number will be assigned to each subject who has provided written pre-screening informed consent. The subject unique identification number will incorporate a three-digit Study Center number (901, 902 or 903....) and a three-digit numeric ID assigned in successive order of entering the study after signing the pre-screening ICF at each center, beginning with 001 at each site (e.g. 901-001 or 902-001).

Subject Screening # :

XXX - YYY

XXX=Study Center

YYY=Subject Numeric ID

Once the pre-screening ICF has been signed, the following procedures and information will be obtained to confirm pre- eligibility including:

- Review of prior medical records
- CCR5+ status confirmed by archival or fresh biopsy from primary or metastatic site

A pre-screening log will be maintained to capture the following information:

- Subject unique identification number
- Patient initials
- Date pre-screened
- Initial eligibility
- Date of re-consent (for the full consent form) or reason for ineligibility

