4.2 SCREENING PERIOD

4.2.1. Screening Visit (SV)

The subject (or Legally Acceptable Representative (LAR)) will sign and date the informed consent form (ICF) and Health Insurance Portability Accountability Act (HIPAA) authorization (according to site policy and practices) prior to any study-related procedures. All study centers will be instructed to maintain the study-specific screening and enrollment logs at their sites. If a subject initially fails to meet inclusion/exclusion criteria and is later reconsidered for participation, the subject will be re-consented and assigned a new unique identification number at the time of re-screening. Subjects who fail their first screening attempt may be re-screened a maximum of once and may be enrolled if they are found to meet all inclusion and no exclusion criteria when re-screened.

Once the Screening ICF has been signed, screening procedures and information will be obtained to confirm subject eligibility including:

- Demographic information and baseline disease characteristics (see [Section 7.3](#)),
- Medical history (see [Section 7.4](#)),
- Prior medications assessment (see [Section 7.5](#)),
- Vital Signs (see [Section 7.6](#)),
- Body Weight & Height measurements (see [Section 7.6](#)),
- Physical examination (see [Section 7.7](#)),
- Eastern Cooperative Oncology Group (ECOG) Performance Review (see [Section 7.8](#))
- 12-lead Electrocardiogram (see [Section 7.9](#))
- Tumor imaging assessment (see [Section 7.15](#))

Note: Prior imaging assessment within the last 3 months of the Screening Visit is acceptable

- Collection of lab specimens (see [Section 7.11](#)) for
 - Complete blood count
 - Biochemistry
 - Serum pregnancy test, for female subjects of childbearing potential.
 - Urine sample for urinalysis parameters

All screening information will be fully documented in the subject's medical records (i.e., source documents).

- For consented subjects who do not meet eligibility criteria, a Screen Failure Case Report Form (CRF) will be completed. The Screen Failure CRF will contain the following details: the subject identification number, the date of ICF signature, demographic information (see [Section 7.3](#)), and the reason for screen failure. No additional information will be required for subjects who fail screening.
- For consented subjects who meet eligibility criteria, all required screening information will be transcribed onto the appropriate page of the CRF.

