7.4 MEDICAL HISTORY

A complete review of the subject's past medical history, past surgeries, and current therapies (medications and non-medications) will be undertaken by the Investigator to check that all inclusion and no exclusion criteria have been met.

Events that emerge prior to the first treatment will be recorded in the medical history and not as AEs. Aside from being used to determine subject eligibility, this information will permit the Investigator to record the nature, duration and severity of any ongoing baseline medical conditions prior to the subject's receiving investigational product treatment.

Medical histories will be recorded using the body system categories outlined below:

• Cardiovascular	• Lymphatic
• Respiratory	• Hematologic
• Gastrointestinal	• Immunologic
• Renal	• Dermatologic
• Hepatic	• Psychiatric
• Neurological	• Genitourinary
• Endocrine	• Other

For each relevant history, the following will be documented:

- Disease/disorder/condition
- Date of diagnosis
- History status (resolved or ongoing).

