8.7.3. Study Analyses

Safety Outcome Measures:

The safety outcome measures in this study are:

- The number, frequency, and severity of adverse events (AEs) collected from the time of first treatment until 12 weeks after study treatment completion to evaluate safety of leronlimab (PRO 140) in subjects with CCR5+ locally advanced or metastatic solid tumors.

Note: Adverse events will follow National Cancer Institute Common Terminology Criteria for Adverse Events (CTCAE) version 5.0

- Laboratory data changes from baseline to subsequent scheduled visits
- Changes in physical examinations from baseline to subsequent scheduled visits
- Changes in vital signs from baseline to subsequent scheduled visits.
- Changes in Eastern Cooperative Oncology Group (ECOG) performance status from baseline to subsequent scheduled visits.
- Changes of electrocardiogram (ECG) results from baseline to subsequent scheduled visits

Efficacy Outcome Measures:

The efficacy outcome measures in this study are:

- Progression free survival (PFS) defined as time in months from the date of first study treatment to the date of disease progression or death from any cause, whichever comes first.

Note: All patients who receive at least one dose of leronlimab (PRO 140) will be included in the primary analyses of PFS. The Response Evaluation Criteria in Solid Tumors (RECIST v1.1) criteria will be used for objective tumor response assessment (when disease is measurable and non- measurable);

The time in months from start of treatment to progression or death will be measured for all patients who receive at least one dose of study drug. Patients will be followed up to 2 years after completion of treatment.

- Overall response rate (ORR, defined as Complete Response (CR) + Partial Response (PR)), and clinical benefit rate (CBR, defined as CR + PR + Stable Disease (SD)) in subjects with CCR5+ locally advanced or metastatic solid tumors treated with leronlimab (PRO 140).

Note: Overall response rate is defined as the proportion of patients who achieve an overall response of complete response or partial response in the total number of evaluable patients, assessed by RECIST v1.1. Clinical benefit rate is defined as the proportion of patients who achieve an overall response of complete response or partial response or stable disease in the total number of evaluable patients, assessed by RECIST v1.1.

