9.4 REPORTING OF SERIOUS ADVERSE EVENTS

The Investigator is required to report all SAEs that occur during the time period specified in [Section 9.2](#). Once the Investigator becomes aware of an SAE, he/she must report the SAE to [REDACTED] within 24 hours:

CRO Medical Monitor	[REDACTED]
	[REDACTED]

A written SAE reports must include a full description of the event as described in [Section 9.2](#) and must follow within 24 hours from the time the Investigator first learned of the event. The [REDACTED] may request additional supporting documentation as it becomes available, such as lab reports, electrocardiogram [ECG] reports, discharge summary, hospital notes, etc, if applicable.

The Investigator is also responsible for reporting all SAEs to the appropriate Institutional Review Board (IRB) in accordance with local laws and regulations. The Investigator is responsible for maintaining documentation in the study file that indicates the IRB has been properly notified.

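### AE and SAE reporting opens at first dose, so complications of a protocol-required fresh CCR5 biopsy that arise before dosing are not captured as AEs or SAEs

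*Protocol*

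**What the plan says.** **Reporting window.** Protocol Section 9.2 states that reporting of all AEs and SAEs "will begin at the time of the first treatment and continue up to the final study visit". Section 9.4 takes its scope from there: "The Investigator is required to report all SAEs that occur during the time period specified in" Section 9.2. Section 9.1 applies the same start to abnormal findings: those judged clinically significant that "occurred after initiation of the first study treatment will be reported as AEs". The AE outcome measure in Section 8.7.3, repeated in SAP Section 2.7.2, covers events "collected from the time of first treatment until 12 weeks after study treatment completion".

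**Earlier events.** Section 7.4: "Events that emerge prior to the first treatment will be recorded in the medical history and not as AEs".

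**The biopsy.** CCR5 tissue staining is mandatory (Section 7.11.1), and willingness to give fresh tissue when no archival tissue exists is inclusion criterion 3 (Section 3.3.1). Section 4.1.1 places the procedure at pre-screening, under its own consent form: "If archival tissue is not available then, fresh core or excisional biopsy will be obtained". Section 1.6.1 names bleeding as the commonest problem and adds: "Rarer complications of core biopsy include infection and abscess formation, pneumothorax". The same paragraph describes serious complications of core biopsy as rare.

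**Patients who are not enrolled.** The pre-screening log in Section 4.1.1 holds an identifier, initials, dates, initial eligibility and the reason for ineligibility. The Screen Failure CRF in Section 4.2.1 holds an identifier, consent date, demographics and reason for failure. That section then says: "No additional information will be required for subjects who fail screening". Sections 5.3 and 11.2 agree.

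**The concern.** The fresh biopsy is an invasive procedure done under a study consent to establish eligibility, so its complications are trial-related harm. The protocol warns of them but places them outside its own reporting period. Some could meet the SAE criteria in Section 9.3, for example a pneumothorax that leads to hospital admission. Under Sections 9.2 and 9.4, such an event before first dose does not call for the 24-hour SAE report. The DSMB, which under Section 12 reviews SAEs and deaths, then has no defined route to it through the trial's safety reporting.

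The patients most exposed to the gap are those biopsied and found CCR5-negative. They carry the procedural risk and receive no study drug.

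**Working it through.** No arithmetic applies: the point concerns when a reporting window opens, and the documents give neither a number of fresh biopsies nor a complication rate. The check sets the provisions against the order of events.

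1. **Order of events** (Synopsis; Protocol Sections 4 and 4.1.1). Pre-screening consent, fresh biopsy if no archival tissue exists, CCR5 result, screening consent and assessments, first dose. The biopsy comes before first dose in every case.

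2. **Length of the interval.** The Synopsis sets no window for pre-screening and allows up to 4 weeks for screening. A complication could arise and resolve before reporting opens.

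3. **Patients later dosed.** Section 7.4 classes a pre-dose complication as medical history. It requires the condition, diagnosis date and status, and mentions nature, duration and severity for ongoing conditions. It does not ask for seriousness or relationship to a study procedure, and it triggers no expedited report. If the condition worsens after dosing, Section 9.1 makes it an AE. If it first appears after dosing, it falls inside the Section 9.2 window.

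4. **Patients not dosed.** There is no first treatment, so the Section 9.2 period does not begin. Neither the log nor the Screen Failure CRF has an event field. Section 4.3 has those who fail eligibility leave without further evaluation.

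5. **Causality.** Section 9.2.3 relates events to study treatment and to standard-of-care chemotherapy or radiotherapy. It has no category for a study procedure.

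6. **Search for an earlier window.**
   - Section 4.5 has adverse events at unscheduled visits noted in the eCRF, but does not change the Section 9.2 start, and Section 11.2 limits screen failures to one CRF page.
   - In the SAP's schedule (Appendix 1), the Adverse Events row starts in the same column as leronlimab administration. The columns of the protocol's Table 4-1 are not aligned in the extracted text, so that row is not relied on.
   - No provision was found that opens reporting earlier for procedure-related events.

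7. **Analysis.** SAP Sections 6.3 and 8.3 base all safety analyses on the Safety population, meaning dosed subjects. An event in a biopsied patient who was not dosed would have no place in the planned safety outputs even if a site volunteered it.

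**The case against.** The strongest reply is that the safety measures are about leronlimab, and starting AE collection at first dose suits that purpose. That is right for the TEAE tables, which should not change. It does not explain leaving out harm from an invasive procedure that the protocol itself requires.

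A reader might infer that biopsy harm vanishes altogether, or that no oversight body could learn of it. The documents do not support that:

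- Section 14.1 makes the medical record the primary source document, and Section 4.2.1 has screening information documented there. The event would exist at the site.
- Dosed patients would have it in medical history, and later onset or worsening is covered (steps 3 and 6 above).
- The IRB sentence in Section 9.4 is separate from the sponsor-reporting sentence. It refers to local laws and regulations and does not repeat the Section 9.2 window, so a site might report to its IRB.
- The DSMB charter and the pre-screening consent form were not available to read.

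A reader might also infer a large number of lost SAEs. Fresh biopsy is the fallback to archival tissue, its frequency is not stated, and Section 1.6.1 calls serious core-biopsy complications rare. No probability can be derived from the documents.

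Finally, the tempting remedy of collecting every SAE from pre-screening consent goes too far. Pre-screening has no set length and the candidates have advanced cancer. Such a rule would gather unrelated hospital admissions, including in patients whose archival tissue spared them a biopsy.

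**Conclusion.** The gap is real and follows from explicit rules, not from silence or ambiguity. Complications of a protocol-required fresh biopsy that arise before first dose are not captured as AEs or SAEs in the trial database, and Section 9.4 does not require their 24-hour report. For biopsied patients who are not dosed, the reporting window does not open and the trial forms have no field for the event.

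Its extent is limited to patients without archival tissue, a group the documents do not count. It includes CCR5-negative patients, who are additional to the up to 30 enrolled. No efficacy estimate and no treatment-emergent safety table is affected. What is lost is trial-level capture and expedited reporting of procedural harm. The conclusion assumes that sites follow Sections 9.2, 9.4 and 7.4 as written and that no document outside the protocol and SAP adds a reporting duty. It should be corrected by amendment because it concerns participant safety and the remedy is cheap.

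**What to change.** **Protocol**

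- Amend Sections 9.2, 9.4 and 7.4 so that AEs and SAEs related to a protocol-required procedure, chiefly the fresh biopsy, are recorded from the time of that procedure for a stated period or until first dose. The SAEs among them should be reported within 24 hours. State that this includes patients who fail pre-screening or screening. The sponsor should set the length of the period.
- Allow a relationship to a study procedure to be recorded under Section 9.2.3.
- Add an event field to the Screen Failure CRF, align the wording in Sections 4.2.1 and 11.2, and make sure the form is completed for patients who fail at pre-screening.

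**SAP**

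- Add a separate pre-treatment listing of these events, not restricted to the Safety population.
- Leave full AE collection and the TEAE definition at first dose.

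**Cost.** A short amendment, one CRF field, one listing and a few extra reports. Biopsied screen failures may need a follow-up phone contact, because a late infection would not otherwise come to the site's notice.
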